8.2.4 End of Treatment and Follow-up Tumor Imaging

In participants who discontinue study intervention, tumor imaging should be performed at the time of intervention discontinuation (± 4 -week window). If previous imaging was obtained within 4 weeks prior to the date of discontinuation, then imaging at intervention discontinuation is not mandatory. For participants who discontinue study intervention due to documented disease progression by RECIST 1.1, this is the final required tumor imaging if the investigator elects to not implement iRECIST.

8.2.5 iRECIST 1.1 Assessment of Disease

iRECIST is based on RECIST 1.1, but adapted to account for the unique tumor response seen with immunotherapeutic drugs. iRECIST will be used by investigator/local radiology reviewers to assess tumor response and progression, and to make treatment decisions. When clinically stable, participants should not be discontinued until progression is confirmed by the investigator, working with local radiology, according to the rules outlined below. This allowance to continue treatment despite initial radiologic PD takes into account the observation that some participants can have a transient tumor flare in the first few months after the start of immunotherapy, and then experience subsequent disease response. These data will be collected and captured in the clinical database.

For participants who show evidence of radiological PD by RECIST 1.1 as determined by the investigator, the investigator will decide whether to continue a participant on study

intervention until repeat imaging is obtained (using iRECIST for participant management (see [Table 18](#) and [Figure 3](#)). This decision by the investigator should be based on the participant's overall condition.

Clinical stability is defined as the following:

- Absence of symptoms and signs indicating clinically significant progression of disease
- No decline in ECOG performance status
- No requirements for intensified management, including increased analgesia, radiation, or other palliative care

Any participant deemed clinically unstable should be discontinued from study intervention at site-assessed first radiologic evidence of PD and is not required to have repeat imaging for confirmation of PD by iRECIST.

If the investigator decides to continue treatment, the participant may continue to receive study intervention and the tumor assessment should be repeated 4 to 8 weeks later to confirm PD by iRECIST per investigator assessment.

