
Tumor flare may manifest as any factor causing radiographic progression per RECIST 1.1, including:

- Increase in the sum of diameters of target lesion(s) identified at baseline to $\geq 20\%$ and ≥ 5 mm from nadir

Note: the iRECIST publication uses the terminology “sum of measurements”, but “sum of diameters” will be used in this protocol, consistent with the original RECIST 1.1 terminology.

- Unequivocal progression of non-target lesion(s) identified at baseline
- Development of new lesion(s)

iRECIST defines new response categories, including iUPD (unconfirmed progressive disease) and iCPD (confirmed progressive disease). For purposes of iRECIST assessment, the first visit showing progression according to RECIST 1.1 will be assigned a visit (overall) response of iUPD, regardless of which factors caused the progression.

At this visit, target and non-target lesions identified at baseline by RECIST 1.1 will be assessed as usual.

New lesions will be classified as measurable or nonmeasurable, using the same size thresholds and rules as for baseline lesion assessment in RECIST 1.1. From measurable new lesions, up to 5 lesions total (up to 2 per organ), may be selected as New Lesions – Target.

The sum of diameters of these lesions will be calculated, and kept distinct from the sum of diameters for target lesions at baseline. All other new lesions will be followed qualitatively as New Lesions – Non-target.

Assessment at the Confirmatory Imaging

On the confirmatory imaging, the participant will be classified as progression confirmed (with an overall response of iCPD), or as showing persistent unconfirmed progression (with an overall response of iUPD), or as showing disease stability or response (iSD/iPR/iCR).

Confirmation of Progression

Progression is considered confirmed, and the overall response will be iCPD, if ANY of the following occurs:

- Any of the factors that were the basis for the initial iUPD show worsening:

For target lesions, worsening is a further increase in the sum of diameters of ≥ 5 mm, compared to any prior iUPD time point

For nontarget lesions, worsening is any significant growth in lesions overall, compared to a prior iUPD time point; this does not have to meet the “unequivocal” standard of RECIST 1.1

For new lesions, worsening is any of these:

- An increase in the new lesion sum of diameters by ≥ 5 mm from a prior iUPD time point
- Visible growth of new non-target lesions
- The appearance of additional new lesions

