- Any new factor appears that would have triggered PD by RECIST 1.1

Persistent iUPD

Progression is considered not confirmed, and the overall response remains iUPD, if:

- None of the progression-confirming factors identified above occurs AND
- The target lesion sum of diameters (initial target lesions) remains above the initial PD threshold (by RECIST 1.1)

Additional imaging for confirmation should be scheduled 4 to 8 weeks from the imaging on which iUPD is seen. This may correspond to the next visit in the original visit schedule. The assessment of the subsequent confirmation scan proceeds in an identical manner, with possible outcomes of iCPD, iUPD, and iSD/iPR/iCR.

Resolution of iUPD

Progression is considered not confirmed, and the overall response becomes iSD/iPR/iCR if:

- None of the progression-confirming factors identified above occurs, AND
- The target lesion sum of diameters (initial target lesions) is not above the initial PD threshold

The response is classified as iSD or iPR (depending on the sum of diameters of the target lesions), or iCR if all lesions resolve.

In this case, the initial iUPD is considered to be pseudoprogression, and the level of suspicion for progression is “reset”. This means that the next visit that shows radiographic progression, whenever it occurs, is again classified as iUPD by iRECIST, and the confirmation process is repeated before a response of iCPD can be assigned.

Management Following the Confirmatory Imaging

If repeat imaging does not confirm PD per iRECIST, as assessed by the investigator, and the participant continues to be clinically stable, study intervention may continue and follow the regular imaging schedule. If PD is confirmed, participants will be discontinued from study intervention.

Note: If a participant has confirmed radiographic progression (iCPD) as defined above, but the participant is achieving a clinically meaningful benefit, an exception to continue treatment may be considered following consultation with the Sponsor. In this case, if study intervention is continued, tumor imaging should continue to be performed following the intervals as outlined in the SoA and submitted to the central imaging vendor.

Detection of Progression at Visits after Pseudoprogression Resolves

After resolution of pseudoprogression (ie, achievement of iSD/iPR/iCR), iUPD is indicated by any of the following events:

- Target lesions

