Sum of diameters reaches the PD threshold (20% and 5 mm increase from nadir) either for the first time, or after resolution of previous pseudoprogression. The nadir is always the smallest SOD seen during the entire study, either before or after an instance of pseudoprogression.

- Non-target lesions

If non-target lesions have never shown unequivocal progression, their doing so for the first time results in iUPD

If non-target lesions had shown previous unequivocal progression, and this progression has not resolved, iUPD results from any significant further growth of non-target lesions, taken as a whole

- New lesions

New lesions appear for the first time

Additional new lesions appear

Previously identified new target lesions show an increase of ≥ 5 mm in the new lesion sum of diameters, from the nadir value of that sum

Previously identified non-target lesions show any significant growth

If any of the events above occur, the overall response for that visit is iUPD, and the iUPD evaluation process (see Assessment at the Confirmatory Imaging above) is repeated. Progression must be confirmed before iCPD can occur.

The decision process is identical to the iUPD confirmation process for the initial PD, with one exception: if new lesions occurred at a prior instance of iUPD, and at the confirmatory imaging the burden of new lesions has increased from its smallest value (for new target lesions, the sum of diameters is ≥ 5 mm increased from its nadir), then iUPD cannot resolve to iSD or iPR. It will remain iUPD until either a decrease in the new lesion burden allows resolution to iSD or iPR, or until a confirmatory factor causes iCPD factors above indicate iUPD, the iUPD evaluation process repeats, just as on the first occurrence of iUPD. iUPD must be confirmed before iCPD can occur.

[figure not shown]
Additional details about iRECIST are provided in the iRECIST publication [Eisenhauer, E. A., et al 2009] [Seymour, L., et al 2017].

Table 18 Imaging and Treatment after First Radiologic Evidence of Progressive Disease

	Clinically Stable		Clinically Unstable	
	Imaging	Treatment	Imaging	Treatment
First radiologic evidence of PD by RECIST 1.1	Repeat imaging at 4 to 8 weeks to confirm PD	May continue study intervention at the local site investigator's discretion while awaiting confirmatory tumor imaging by site by iRECIST	Repeat imaging at 4 to 8 weeks to confirm PD per physician discretion only	Discontinue treatment

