9.4 Analysis Endpoints

9.4.1 Efficacy/Immunogenicity/Pharmacokinetics Endpoints

OR is a confirmed CR or PR based on RECIST 1.1 by the investigator. OR is primary endpoint for the 3 cohorts in Arm 1 and is secondary endpoint for the 2 cohorts in Arm 2 Part II. ORR is the proportion of participants with OR.

[figure not shown]
PFS is defined as the time from the first dose of study treatment to the first documented PD based on RECIST1.1 by the investigator or death due to any cause, whichever occurs first. PFS is secondary endpoint for the 3 cohorts in Arm1.

DOR is defined as the time from the first documented evidence of CR or PR until PD based on RECIST1.1 by the investigator or death due to any cause, whichever occurs first, in participants demonstrating PR or CR. DOR is secondary endpoint for the 3 cohorts in Arm1.

OR, PFS and DOR are also evaluated based on iRECIST by the investigator.

OS is defined as the time from the first dose of study treatment to death due to any cause. Participants who do not die will be censored on the date of the last study assessment or contact. Overall survival is a secondary endpoint for Arm 1.

CCI

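### At a first iUPD caused only by new or non-target lesions, an unchanged repeat scan is classed as resolved, which may bias the secondary iRECIST endpoints upward

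*Combined protocol and SAP*

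**What the plan says.** Section 8.2.5 opens the iRECIST process at the first visit with RECIST 1.1 progression. That visit "will be assigned a visit (overall) response of iUPD, regardless of which factors caused the progression". The possible causes are growth of the target sum, unequivocal non-target progression and new lesions.

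At the repeat scan the section first looks for confirming factors: further target growth, any significant non-target growth, a rise of at least 5 mm in the new-lesion sum, visible growth of new non-target lesions, additional new lesions, or any fresh RECIST 1.1 trigger. Any of these gives confirmed progression (iCPD). If none occurs, two outcomes remain:

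- Persistent iUPD, if "The target lesion sum of diameters (initial target lesions) remains above the initial PD threshold (by RECIST 1.1".
- Resolution to iSD, iPR or iCR, if "The target lesion sum of diameters (initial target lesions) is not above the initial PD threshold".

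After resolution, iSD and iPR are told apart by the target sum, while iCR needs every lesion to resolve. The text adds: "In this case, the initial iUPD is considered to be pseudoprogression". The next progression then starts a new iUPD that needs its own confirmation.

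For later episodes the section keeps the same process with one exception. If new lesions occurred at an earlier iUPD and their burden has risen from its smallest value, iUPD cannot resolve to iSD or iPR until that burden falls.

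On endpoints, Section 9.4.1 says: "OR, PFS and DOR are also evaluated based on iRECIST by the investigator". Section 3 makes iRECIST ORR, PFS and DOR secondary in Arm 1 and iRECIST ORR secondary in Arm 2. Section 9.6.1 leaves the PFS and DOR censoring rules to the sSAP.

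**The concern.** A first iUPD can have three kinds of cause, but once nothing has worsened, the decision that it has gone away looks at only one of them. If the cause was a new lesion or non-target progression and the repeat scan is the same, the lesion that raised the alarm is still there and no smaller. The visit is nevertheless recorded as pseudoprogression, and iPR can be assigned while a new lesion persists.

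This fits poorly with the section's own reason for the scheme, that "some participants can have a transient tumor flare in the first few months after the start of immunotherapy, and then experience subsequent disease response". An unchanged scan shows neither a transient flare nor a response. The section also foresees the situation. Under its heading on progression after pseudoprogression has resolved, it has a case that begins: "If non-target lesions had shown previous unequivocal progression, and this progression has not resolved".

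At stake is whether the investigator-assessed iRECIST results of an uncontrolled study look better than the RECIST 1.1 results partly because of this classification step.

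**Working it through.** **1. The rule at a first iUPD, set against an alternative.** Inputs: the confirmation, persistence and resolution conditions of Section 8.2.5. The alternative keeps iUPD while the new or non-target lesion that caused it has not regressed. The rows are for an iUPD with a new or non-target cause.

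| Target sum at repeat scan | New / non-target lesions | As written | Alternative |
|---|---|---|---|
| Above threshold | Worse | iCPD | iCPD |
| Above threshold | Unchanged | iUPD | iUPD |
| Above threshold | Gone | iUPD | iUPD |
| Not above | Worse | iCPD | iCPD |
| Not above | **Unchanged** | **iSD/iPR, reset** | **iUPD** |
| Not above | Gone | Resolved | Resolved |

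The two rules differ in one row. With a new-lesion-only or non-target-only cause, the target sum was not above the threshold at the iUPD visit. If it first crosses at the repeat scan, that is a fresh trigger and gives iCPD. So for these causes persistent iUPD cannot be reached. For measurable new lesions, unchanged here includes a rise of less than 5 mm in their sum, because only 5 mm or more counts as worsening.

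**2. First against later episode.** Suppose new lesions caused the iUPD, the repeat scan is unchanged and the target sum is not above the threshold. At a first episode this is resolved. At a later episode that began with a rise of at least 5 mm from the nadir of the new-lesion sum, it stays iUPD until the burden falls. No reason is given for the difference. The exception covers new lesions only.

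**3. Effect on ORR.** The plan's own figures come first. Table 20 uses the Clopper-Pearson interval: lower limit = Beta quantile 0.025 (x, n − x + 1), upper limit = Beta quantile 0.975 (x + 1, n − x). With n = 30 and x = 6 this gives 20.0% (7.7%, 38.6%), as printed. All eight rows of the table reproduce to 0.1 point.

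One more confirmed responder adds 1/30 = 3.3 points. For example, 6/30 = 20.0% (7.7%, 38.6%) becomes 7/30 = 23.3% (9.9%, 42.3%). The documents give no frequency. Assuming 0 to 3 such participants per cohort, the rise is 0 to 10 points; with three, 9/30 = 30.0% (14.7%, 49.4%). A participant counts only if the target sum also meets iPR and the response is confirmed.

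**4. Effect on PFS and DOR.** Illustration: new lesion at week 9, identical scan at week 13, new-lesion sum up by at least 5 mm at week 18.

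- As written: resolved at week 13, a new iUPD at week 18, and iCPD at the earliest at the next repeat scan 4 to 8 weeks later (18 + 4 = 22 to 18 + 8 = 26).
- Alternative: iUPD at weeks 9 and 13, iCPD at week 18.

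| Event dated at | As written | Alternative | Shift |
|---|---|---|---|
| iCPD | week 22–26 at the earliest | week 18 | at least 4–8 weeks |
| iUPD opening the confirmed episode | week 18 | week 9 | 9 weeks |
| First RECIST 1.1 progression | week 9 | week 9 | 0 |

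The supplied text does not say which date applies.

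**The case against.** The strongest reply is that the rule looks deliberate. Section 8.2.5 says the confirmatory scan may show stability as well as response, so treating an unchanged scan as non-progression is stated policy. The wording on non-target progression that has not resolved sets a lower bar, any significant further growth, for catching it later. New lesions are likewise followed from the nadir of their sum, so slow growth accumulates and is eventually caught. All of this is fair. It does not explain why an unchanged new-lesion burden is handled differently at first and later episodes, and catching growth later does not undo an iPR or a reset already recorded.

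Three stronger readings are tempting and are not supported:

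- A reader might infer that target size alone decides resolution, so that any new-lesion or non-target progression is cleared. Worsening in any lesion class gives iCPD before the target sum is considered, and iCR needs all lesions to resolve.
- A reader might infer that a known share of first progressions is cleared. The documents give no share of progressions without a target component, and such a share would apply in full only if every repeat scan were unchanged.
- A reader might infer that PFS is always delayed by at least one imaging interval. With dating at first RECIST 1.1 progression the shift in the example is zero. At the repeat scan itself no event is lost, since persistent iUPD is not confirmed progression either.

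Whether the rule departs from the published iRECIST guideline cannot be checked from these documents, and the point does not rest on it.

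The reach is also limited. The study is for estimation, RECIST 1.1 results are reported alongside, and early termination with removal of follow-up imaging will reduce the number of affected assessments.

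**Conclusion.** The point holds in a narrow form. At a first iUPD caused only by new or non-target lesions, a repeat scan on which nothing meets a worsening criterion is classed iSD or iPR and reset, even if the triggering lesions have not regressed. The later-episode exception treats new-lesion burden more strictly, with no stated reason.

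Compared with a rule that keeps an unregressed trigger at iUPD, no participant's iRECIST response, progression time or response duration becomes less favourable, and some may become more favourable. The possible bias is therefore upward. One caution on reading: median DOR is taken over responders, so it also reflects who is added to that group.

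The size is 3.3 ORR points per added confirmed responder in a cohort of 30. In the one worked example the progression date moves by 0 to 9 weeks; where the event is dated at iCPD, the 4 to 8 weeks are minimum values. The number of affected participants is unknown and may be zero. The primary Arm 1 ORR, which uses RECIST 1.1, is untouched. The point merits correction because the fix is cheap, but it does not threaten the study's main result.

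**What to change.** For endpoint derivation only:

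1. Reconcile the first-episode resolution rule in Section 8.2.5 with the later-episode exception for new lesions, or state why they differ.
2. In deriving iRECIST OR, PFS and DOR, count an iUPD as resolved only if no confirming factor occurs and the factor that triggered it has regressed: target sum no longer above the threshold, non-target progression no longer unequivocal, new-lesion burden decreased or gone. Define operationally what counts as decreased. At minimum, report this as a sensitivity derivation beside the rule as written.
3. State the event date for iRECIST PFS and DOR: first RECIST 1.1 progression, the iUPD that opens the confirmed episode, or iCPD.

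The lesion data already collected are enough for this. The cost is some extra programming and possibly slightly less favourable iRECIST estimates.

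Section 8.2.5 and Table 18 also tie treatment and repeat imaging to whether a visit is iUPD or iSD/iPR. Repeat imaging falls at 4 to 8 weeks for iUPD and on the regular schedule otherwise, and treatment actions differ for clinically unstable participants. The sponsor must reconcile that wording with any change. No clinical rule is proposed here.

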8.2.6 Eastern Cooperative Oncology Group Performance Scale

The investigator or qualified designee will assess ECOG status at screening, prior to the administration of each dose of study intervention, and during the follow-up period as specified in the SoA.

8.3 Safety Assessments

Details regarding specific safety procedures/assessments to be performed in this study are provided. The total amount of blood/tissue to be drawn/collected during of the study (from prestudy to poststudy visits), including approximate blood/tissue volumes drawn/collected by visit and by sample type per participant, can be found in Section 8.3.6.1.

Planned time points for all safety assessments are provided in the SoA.

8.3.1 Physical Examinations

8.3.1.1 Full Physical Examination

The investigator or qualified designee will perform a complete physical exam during the Screening period. Clinically significant abnormal findings should be recorded as medical history. The time points for full physical exams are described in the SoA. After the first dose of study intervention, new clinically significant abnormal findings should be recorded as AEs.

Investigators should pay special attention to clinical signs related to previous serious illnesses.

8.3.1.2 Directed Physical Examination

For cycles that do not require a full physical exam as defined in the SoA, the investigator or qualified designee will perform a directed physical exam as clinically indicated prior to study intervention administration. New clinically significant abnormal findings should be recorded as AEs.

Investigators should pay special attention to clinical signs related to previous serious illnesses.

8.3.2 Vital Signs

The investigator or qualified designee will take vital signs at screening, prior to the administration of each dose of study intervention and during the follow-up period as specified in the SoA. Vital signs include temperature, pulse, respiratory rate and blood pressure. Weight will be obtained as specified in the SoA. Height will be measured at screening only.

8.3.3 Electrocardiograms

A standard 12-lead ECG will be performed using local standard procedures. The timing of ECGs is specified in the SoA. Clinically significant abnormal findings should be recorded as medical history. Additional ECGs may be performed as clinically necessary.

8.3.4 Endoscopy: Required for Arm 2 Part II, Cohort D only

An endoscopy will be performed using local standard procedures at screening for esophageal varices, unless such screening has been performed in the past 12 months prior to C1D1.

